1 GENERAL INFORMATION

This study is being performed to assess the relative effectiveness of the COOLIEF™ Pain Management System (formerly owned by Halyard Health, and now owned by Avanos Medical; Alpharetta GA) to manage moderate to severe knee pain in patients with osteoarthritis (OA) of the knee when compared to a single Viscosupplementation injection. The product under study is currently marketed in the United States and has been cleared via 510(k) by the FDA under application K053082 and K163461 in combination with the Halyard Radiofrequency (RF) Generator (PMG-115-TD/PMG-230-TD, or PMG-BASIC/PMG-ADVANCED K072478) for use in creating radiofrequency lesions in nervous tissue. It is also indicated for creating radiofrequency lesions of the genicular nerves for the management of moderate to severe knee pain of more than 6 months with conservative therapy, including medication, in patients with radiographically-confirmed osteoarthritis (grade 2-4) and a positive response (≥ 50% reduction in pain) to a diagnostic genicular nerve block.

A Long-Term Extension will capture data allowing the assessment of the long term clinical outcomes (such as current level of pain, function, and progression of disease) for patients who received COOLIEF* as their initial treatment. Subjects who received COOLIEF* as their initial treatment will be asked to return for 2 additional visits representing 18 and 24 months post initial treatment.

Investigator Acknowledgement Signature Page

Title: A Prospective, Multi-center, Randomized, Clinical Trial Evaluating the Safety and Effectiveness of Using COOLIEF™ Cooled Radiofrequency Probe to Create Lesions of the Genicular Nerves and Comparing a Single Injection of Hyaluronic Acid in the Management of Knee Pain

I have read the attached protocol and agree that it contains all the necessary details for performing the study. I agree to conduct the study according to the protocol.

[figure not shown]
I will provide copies of the protocol and of the pre-clinical information on the Study Device (e.g., Investigator Brochure or Report of Prior Investigations) that was furnished to me by the Sponsor to all members of the study team responsible to me. I will discuss this material with them to assure that they are fully informed regarding the Study Device and the conduct of the study.

- 5. Positive response (defined as a decrease in numeric pain scores of at least 50%) to a single genicular nerve block of the index knee
- 6. Pain on NRS ≥ 6 on an 11-point scale for the index knee
- 7. Radiologic confirmation of arthritis (x-ray/MRI/CT) of OA grade of 2 (mild), 3 (moderate) or 4 (severe) noted within 6 months for the index knee
- 8. An intra-articular hyaluronic acid injection is indicated as an appropriate treatment option
- WOMAC Knee Score group at baseline of Score of ≥ 2 (0 to 4 scale) on WOMAC question 1 (Pain) and a mean score of ≥ 1.5 on all five questions of the WOMAC pain subscale.
- 10. Analgesics including membrane stabilizers such as Neurontin/gabapentin and antidepressants for pain such as Cymbalta duloxetine must be clinically stable (defined as stable dosage for ≥ 6 weeks prior to the screening visit) and shall not change during the course of the study without approval of the investigator
- 11. Agree to see one physician (study physician) for knee pain during the study period
- 12. Willing to utilize double barrier contraceptive method if of child bearing potential
- 13. Willing to delay any surgical intervention for the index knee for the period of the study follow up
- 14. Willingness to provide informed consent and to comply with the requirements of this protocol for the full duration of the study

Exclusion Criteria

- 1. Evidence of inflammatory arthritis (for example, rheumatoid arthritis) or other systemic inflammatory condition (for example, gout, fibromyalgia) that could cause knee pain
- 2. Evidence of neuropathic pain affecting the index knee
- 3. Previous or pending lower limb amputation
- 4. Intra-articular steroid injection into the index knee within 90 days from randomization
- 5. Hyaluronic acid injection, platelet rich plasma (PRP), stem cell, or arthroscopic debridement/lavage injection into the index knee within 180 days from randomization
- 6. Prior radiofrequency ablation of the genicular nerves of the index knee
- 7. Prior partial, resurfacing, or total knee arthroplasty of the index knee (residual hardware)
- 8. Clinically significant ligamentous laxity of the index knee
- Clinically significant valgus/varus deformities or evidence of pathology (other than osteoarthritis of knee) that materially affects gait or function of the knee or is the underlying cause of the knee pain and/or functional limitations
- 10. Body mass index (BMI) > 40 kg/m^2

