7.1 INCLUSION CRITERIA

- 1. Age ≥ 21 years
- 2. Able to understand the informed consent form and provide written informed consent and able to complete outcome measures
- 3. Chronic knee pain for longer than 6 months that interferes with functional activities (for example, ambulation, prolonged standing, etc.)
- Continued pain in the target knee despite at least 3 months of conservative treatments, including activity modification, home exercise, protective weight bearing, and/or analgesics (for example, acetaminophen or non-steroidal anti-inflammatory drugs [NSAIDs])
- 5. Positive response (defined as a decrease in numeric pain scores of at least 50%) to a single genicular nerve block of the index knee
- 6. Pain on NRS ≥ 6 on an 11-point scale for the index knee
- 7. Radiologic confirmation of arthritis (x-ray/MRI/CT) of OA grade of 2 (mild), 3 (moderate) or 4 (severe) noted within 6 months for the index knee
- 8. An intra-articular hyaluronic acid injection is indicated as an appropriate treatment option
- WOMAC Knee Score group at baseline of Score of ≥ 2 (0 to 4 scale) on WOMAC question 1 (Pain) and a mean score of ≥ 1.5 on all five questions of the WOMAC pain subscale.
- 10. Analgesics including membrane stabilizers such as Neurontin/gabapentin and antidepressants for pain such as Cymbalta/duloxetine must be clinically stable (defined as stable dosage for ≥ 6 weeks prior to the screening visit) and shall not change during the course of the study without approval of the investigator
- 11. Agree to see one physician (study physician) for knee pain during the study period
- 12. Willing to utilize double barrier contraceptive method if of child bearing potential.
- 13. Willing to delay any surgical intervention for the index knee for the period of the study follow up
- 14. Willingness to provide informed consent and to comply with the requirements of this protocol for the full duration of the study

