7.2 EXCLUSION CRITERIA

- 1. Evidence of inflammatory arthritis (for example, rheumatoid arthritis) or other systemic inflammatory condition (for example, gout, fibromyalgia) that could cause knee pain
- 2. Evidence of neuropathic pain affecting the index knee
- 3. Previous or pending lower limb amputation
- 4. Intra-articular steroid injection into the index knee within 90 days from randomization

- 5. Hyaluronic acid injection, platelet rich plasma (PRP), stem cell, or arthroscopic debridement/lavage injection into the index knee within 180 days from randomization
- 6. Prior radiofrequency ablation of the genicular nerves of the index knee
- 7. Prior partial, resurfacing, or total knee arthroplasty of the index knee (residual hardware)
- 8. Clinically significant ligamentous laxity of the index knee
- Clinically significant valgus/varus deformities or evidence of pathology (other than osteoarthritis of knee) that materially affects gait or function of the knee or is the underlying cause of the knee pain and/or functional limitations
- 10. Body mass index (BMI) > 40 kg/m²
- 11. Extremely thin patients and those with minimal subcutaneous tissue thickness that would not accommodate a radiofrequency lesion of up to 14 mm in diameter to limit the risk of skin burns
- 12. Pending or active compensation claim, litigation or disability remuneration (secondary gain)
- 13. Pregnant, nursing or intent on becoming pregnant during the study period
- 14. Chronic pain associated with significant psychosocial dysfunction
- 15. Beck's Depression Index score of > 22 (indicates clinically depressed state)
- 16. Allergies to any of the medications to be used during the procedures, including known hypersensitivity (allergy) to hyaluronate preparations or allergies to avian or avian-derived products (including eggs, feathers, or poultry)
- 17. Active joint infection or systemic or localized infection at needle entry sites (subject may be considered for inclusion once infection is resolved)
- 18. History of uncontrolled coagulopathy, ongoing coagulation treatment that cannot be safely interrupted for procedure, or unexplained or uncontrollable bleeding that is uncorrectable.
- 19. Identifiable anatomical variability that would materially alter the procedure as described in the protocol
- 20. Within the preceding 2 years, subject has suffered from active narcotic addiction, substance, or alcohol abuse

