8.4.2 Index Knee

The "index" knee is defined as the knee that is being studied and to which the eligibility criteria are applied. This is the knee that will be treated with either CRFA or HA injection. Subjects may have moderate osteoarthritis in the contralateral limb and still be included in the clinical trial; however, only one knee may meet eligibility and be entered into the study.

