8.4.4 Subject Reported Clinical Symptoms of Chronic Knee Pain

All subjects are required to complete a Numeric Rating Scale²⁴ (NRS) for pain at multiple points during the clinical study. Subjects will be asked to rate their usual pain, worst pain, least pain, and current pain in each knee at each time point. An NRS of \geq 6 (usual daily pain) for their index knee is required for entrance in the study. An accurate assessment of NRS is critical at all points in the study, especially at the 6-month visit, as this will be used as the primary endpoint of the study.

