8.4.5 Combined Investigator/Subject Reported Outcomes

The WOMAC is a disease-specific validated outcomes instrument that is routinely used to evaluate the overall condition of subjects with osteoarthritis of the knee²⁵. This instrument assesses pain, stiffness and physical function subscales and requires inputs from both the subject and the investigator.

For study inclusion, WOMAC Knee Score group at baseline of Score of 2 or 3 (0 to 4 scale) on WOMAC question A1 (pain while walking on flat surface) and a mean score of 1.5 to 3.5 on all five questions of the WOMAC subscale A (pain) are required.

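### Section 8.4.2 implies a limit on the other knee that the eligibility lists lack, leaving severe contralateral OA unclassified; separately, an already collected baseline covariate goes unused

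*Combined protocol and SAP*

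**What the plan says.** In the synopsis and in 7.1, the nerve-block, pain and radiographic criteria (items 5, 6 and 7) are each tied to the index knee, for example "Pain on NRS ≥ 6 on an 11-point scale for the index knee" and "OA grade of 2 (mild), 3 (moderate) or 4 (severe) noted within 6 months for the index knee". Item 9, the WOMAC criterion, names no knee. In 7.2, exclusion 3 (lower limb amputation) reaches either limb. Exclusion 9 names no particular knee and covers "evidence of pathology (other than osteoarthritis of knee) that materially affects gait or function of the knee", so osteoarthritis itself is exempt from its pathology clause. Neither list sets a ceiling on osteoarthritis or pain in the other knee.

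Section 8.4.2 first defines the index knee as the one under study, to which the entry criteria apply. It then adds: "Subjects may have moderate osteoarthritis in the contralateral limb and still be included in the clinical trial; however, only one knee may meet eligibility".

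On measurement, 8.4.4 states "Subjects will be asked to rate their usual pain, worst pain, least pain, and current pain in each knee at each time point", and Visit 1 includes an NRS assessment. Section 8.4.5 describes the WOMAC as "routinely used to evaluate the overall condition of subjects with osteoarthritis of the knee" and gives no instruction to answer for the index knee; 8.4.8 gives none for the GPE. The planned ANOVAs for WOMAC (12.6.2.2) and for EQ-5D-5L and GPE (12.6.3) contain treatment and center, with an optional interaction.

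**The concern.** Up to 15 centers will screen from this protocol. If one takes 8.4.2 as an entry condition and another works only from 7.1/7.2, they may enrol different subjects. The same uncertainty reaches the analysis sets. Section 12.1.2 has the sponsor grade violations of the entry criteria as minor or major, and major ones leave the Per-Protocol Set. Where the protocol does not settle whether a criterion was broken, the grading becomes a judgement, and it need only be made before database lock.

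The modelling point is separate and smaller. Each treatment is given to one knee. If the other knee also hurts, it can add variation to outcomes that reflect the whole person. The plan records that pain at baseline and uses it in no analysis.

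**Working it through.** **Step 1: test subjects against the texts.** The plan states no figure on this point, so the check is a comparison of passages.

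- *Subject A: index knee qualifies, other knee is grade 4.* The synopsis and 7.1/7.2 contain nothing that excludes A on the grade of the other knee. Section 8.4.2 says "Subjects may have moderate osteoarthritis in the contralateral limb and still be included in the clinical trial". Item 7 labels grade 3 moderate and grade 4 severe, so A is beyond what 8.4.2 expressly permits. Read as a permission, 8.4.2 does not exclude A; read as a ceiling, it does. If any grade were acceptable, the word moderate would do no work. Result: ambiguous.
- *Subject B: both knees painful, both grade 2-4.* The lists admit B with one index knee. Section 8.4.2 says "only one knee may meet eligibility and be entered into the study". This can mean one enrolled knee per subject (B eligible) or that two qualifying knees exclude (B not eligible). Item 5 requires a response to a block of the index knee, and no block of the other knee is scheduled, so the second knee would not ordinarily be shown to meet every criterion. Result: the one-knee-per-subject reading fits better; A is the live case.
- *Subject C: WOMAC question 1 score of 4, or pain-subscale mean above 3.5.* Item 9 asks for at least 2 on question 1 and a mean of at least 1.5, with no upper limit, so C passes. Section 8.4.5 asks for 2 or 3 on that question and a mean of 1.5 to 3.5, so C fails. Result: a direct conflict.

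**Step 2: follow the consequence.** Ambiguous eligibility leads to ambiguous deviation status (12.1.2) and so to ambiguous Per-Protocol membership (12.2.3). Under 12.2.3 the Per-Protocol Set serves a secondary analysis of the primary endpoint. All other endpoints use the Full Analysis Set unless the SAP says otherwise, so the WOMAC, EQ-5D-5L and GPE comparisons are untouched by this route.

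**Step 3: cost of the covariate.** Take 134 completers (12.1) and the maximum of 15 centers. Error degrees of freedom with treatment and center: 134 − 1 − 1 − 14 = 118. Adding the baseline other-knee NRS gives 117; adding the baseline value of the outcome as well gives 116.

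**Step 4: possible gain.** Let r be the correlation between the baseline other-knee NRS and the outcome, within arm and center and after any other covariate in the model. The documents do not give r; 0.2 to 0.4 is an assumed range.

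- Share of residual variance removed = r²: 0.2² = 4%; 0.4² = 16%.
- Standard error multiplied by √(1 − r²): √0.96 = 0.98; √0.84 = 0.92.
- Equivalent gain in sample size = 1/(1 − r²) − 1: 1/0.96 − 1 = 4%; 1/0.84 − 1 = 19%.

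**The case against.** The strongest reply is that 8.4.2 is permissive. It says what a subject may have, and its second clause reads naturally as one enrolled knee per subject. That stands, which is why the finding is ambiguity. A reader might infer that such subjects are plainly eligible in one section and plainly barred in another; the wording does not go that far.

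A reader might also infer that the lists place no limit at all on the other limb, or that the WOMAC entry criterion can be met by pain in the wrong knee. Neither holds as stated. Exclusion 3 reaches either limb and exclusion 9 names no knee. The definition in 8.4.2 largely ties item 9 to the index knee. An explicit WOMAC instruction would still remove doubt at follow-up, where that definition does not clearly apply.

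That WOMAC and GPE answers mix both knees is an inference, because the forms are not in the documents. Appendix 2 describes a trial whose entry rule paired target-knee pain on walking with the WOMAC pain subscale, so the instrument can be anchored to one knee. Only the EQ-5D-5L is clearly whole-person, and it is tertiary.

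Finally, section 12 promises a stand-alone SAP that could add covariates. True, but a SAP cannot repair inconsistent entry criteria.

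**Conclusion.** The concern holds as an ambiguity in eligibility. Section 8.4.2 carries other-knee wording that neither criteria list contains, and the status of a subject with severe contralateral OA cannot be settled from the text. What is at risk is consistent enrolment and the Per-Protocol sensitivity analysis of the primary endpoint. The size cannot be given, because the documents do not state how many subjects have disease in both knees.

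The covariate is an optional, nearly free gain in precision: 4-16% of residual variance if r is 0.2-0.4, with no support for that range in the documents.

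Two stronger conclusions are tempting. One is that the untreated knee shrinks the secondary treatment differences by a known amount. Assuming that 20-40% of subjects have an equally painful other knee that halves their improvement gives 0.2 × 0.5 = 10% to 0.4 × 0.5 = 20%, but every input is invented. A baseline main effect would also not restore a diluted difference. The other is that the comparison is biased. Randomization is 1:1, so other-knee pain balances on average; what remains is noise and chance imbalance.

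**What to change.** 1. Choose one other-knee condition, whichever the sponsor intends, and print it in identical words in the synopsis, 7.1/7.2 and 8.4.2. If no limit is intended, reword 8.4.2 to say so. Grade deviations under 12.1.2 against that text alone.
2. State on the WOMAC instructions that answers refer to the index knee, and reconcile item 9 with the different limits in 8.4.5.
3. In 12.6.2.2 and 12.6.3, or in the SAP, add the baseline other-knee usual-pain NRS from Visit 1 as a covariate in the WOMAC, EQ-5D-5L and GPE models. Include the baseline value of the outcome where there is one: WOMAC and EQ-5D-5L have it, and the GPE, first recorded after treatment, does not. Name the covariates before outcomes are compared by arm.

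The cost is a few lines of protocol text and one degree of freedom for the other-knee term, plus one for the baseline outcome value where used. No new data or subjects are needed. If the sponsor settles on a stricter entry condition, some additional screen failures may follow.

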3 LIST OF ABBREVIATIONS AND DEFINITION OF TERMS

Abbreviation	Definition
AE	Adverse Event
SAE	Serious Adverse Event
CRF	Case Report Form
CRFA	COOLIEF™ Radiofrequency Ablation
CFR	US Code of Federal Regulations
Cm	Centimeter
СТА	Clinical Trial Agreement
НА	Synvisc-One (Hylan G-F 20)
IRB	Institutional Review Board
NRS	Numeric Rating Scale
NSAID	Non-steroidal anti-inflammatory drug
OA	Osteoarthritis
PI	Principal Investigator
PDMP	Prescription Drug Monitoring Program
QOL	Quality of Life
RF	Radiofrequency
SOP	Standard Operating Procedure
UADE	Unanticipated Adverse Device Effect

Version #: 4.0

Version Date: 28Mar19

4 INTRODUCTION

4.1 BACKGROUND / STUDY POPULATION

With the population aging in the United States and around the world, chronic knee pain from conditions such as osteoarthritis (OA) is becoming a more prominent problem on the medical landscape. Non-steroidal anti-inflammatory drugs (NSAIDs) are the first line treatment for OA for the purpose of reducing pain and inflammation and allowing for the maintenance of activities. Physical therapy or other exercise-based modalities are also considered to be standards of care in the earliest stages of OA to maintain patient mobility to the extent possible.

While total joint replacement is a well-established terminal treatment for late stage OA of major joints, such as the hip and knee, not all patients are well-suited for this procedure due to issues of age, health, or other factors. In addition, total knee replacement, while generally considered effective, has been associated in at least one study with ongoing moderate to significant pain in up to 53% of patients, with patients in that study noting a median average pain score of 3 of 10 and worst pain score of 5 of 10.1

[figure not shown]
Currently, there are a limited number of treatment options available for patients who are not candidates for total joint replacement and/or for whom drugs are either ineffective or are interfering with their overall quality of life and general health. Corticosteroid injection provides significant short term improvement as far as pain relief ², but multiple treatments are required and the steroid and analgesic medication may actually exacerbate cartilage destruction if used over an extended period of time.³ Viscosupplementation (the injection of protein-based gel/fluids into the joint space to improve synovial fluid viscosity) has shown some moderate effectiveness in some studies,^{4 5} but its clinical utility for knee OA has recently been called into question by the American Academy of Orthopaedic Surgeons (AAOS).⁶

COOLIEF™ (CRFA) is a well-established method for delivering lesions into nervous tissue to accomplish neurotomy procedures. Multiple references exist in the literature noting the clinical outcomes of patients treated with CRFA cooled radiofrequency for pain managing denervation in other anatomic locations, including the sacroiliac joint^{7,8,9,10} and the lumbar spinal disc.^{11,12,13} Recent human studies have started to demonstrate the effects of CRFA when specifically used for genicular neurotomy procedures in patients with chronic knee pain resulting from conditions such as OA¹⁴.

Sensory innervation of the knee joint is accomplished by the articular branches of several nerves, including the femoral, tibial, saphenous, obturator, and common peroneal nerves. As a group, these nerves have been termed "genicular nerves." Radiofrequency-generated lesions of the genicular nerves (i.e., genicular neurotomy) using standard, non-cooled radiofrequency ablation has been defined

in the literature. Choi and colleagues¹⁷ published a prospective, randomized, double-blind controlled trial of genicular neurotomy in a series of 38 elderly OA patients with severe knee pain who had failed conservative therapy but responded to a diagnostic block. In this study, the superomedial and inferomedial branches of the saphenous nerve and the superolateral branch of the femoral nerve were targeted for treatment. The probe placement is demonstrated in the figure below taken from Choi, *et al*. They showed statistically significant improvements in pain, Oxford Knee Score, and global perceived effect when compared to placebo at up to 3 months post treatment. Ikeuchi and colleagues¹⁸ also published a prospective randomized study comparing RF neurotomy to diagnostic block alone. In their study, at 12 weeks post treatment, 44% of the RF group rated "good or excellent" compared to only 12% of the block group. The probe placement and lesioning pattern in the Ikeuchi, *et al* study differed from the method of Choi, *et al*.

A recent sponsored study was completed which compared CRFA to intraarticular steroid injections (IAS) for painful OA of the knee and demonstrated statistically significant improvements in pain, function, and global perceived effect of CRFA at 6¹⁴ and 12 months¹⁹. A subset of those patients were followed through 24 months and it was identified that CRFA has the potential to provide sustained effect through this time period. This potential was previously suggested by Ho 2015 where patients reported 24 months of relief following CRFA when used to ablate the lateral branches that innervate the sacroiliac joint²⁰. The nerve targets were identical to those utilized in the Choi research.

In 2014, Franco²¹ *et al* completed a cadaveric dissection study which confirmed the locations of the genicular nerves identified by Choi *et al* and identified an additional nerve target – the middle branch from the vastus intermedius, which will be incorporated as part of the lesioning for this protocol.

This protocol outlines a prospective, single arm, multicenter study examining pain relief as well as other important clinical efficacy indicators of using CRFA to create lesions of the genicular nerves. The probe placement method and lesioning pattern will include the 3 targets utilized in the Choi *et al* and Davis *et al* with targeting of the superomedial and inferomedial branches of the saphenous nerve and the superolateral branch of the femoral nerve, and will include the additional nerve target identified by Franco et al - middle branch from the vastus intermedius.

[figure not shown]
